1.2.3.2.4. Safety Results

Table 1-3 presents the overall summary of AEs by treatment group. Overall, 80.8% of subjects experienced an AE: 83.5% in the placebo group and 79.8% in the pooled SEL group (79.0%, 84.5%, and 75.9% for SEL 2, 6, and 18, respectively). Adverse events related to study drug occurred in 9.4% (8 subjects) in the placebo group and 12.5% (31 subjects) in the pooled SEL group (8.6%, 11.9%, and 16.9% for SEL 2, 6, and 18 mg, respectively). Adverse events leading to study drug discontinuation occurred in 9.4% (8 subjects) in the placebo group compared with 12.1% (30 subjects) in the pooled SEL group (8.6%, 13.1%, and 14.5% for SEL 2, 6, and 18 mg, respectively). Overall, 4 deaths occurred (1.2%), with a frequency of 1.2% in the placebo group and 1.2% in the pooled SEL group (1.2%, 1.2%, and 1.2% for SEL 2, 6, and 18 mg, respectively). Three of the deaths were nontreatment emergent, i.e., occurred more than 30 days after the last dose of study drug.

Table 1-3. GS-US-223-1015: Overall Summary of Adverse Events (Safety Analysis Set)

Number (%) of Subjects With Any	SEL 2 mg (N = 81)	SEL 6 mg (N = 84)	SEL 18 mg (N = 83)	SEL Pooled (N = 248)	Placebo (N = 85)
AE	64 (79.0%)	71 (84.5%)	63 (75.9%)	198 (79.8%)	71 (83.5%)
Grade \geq 3 AE	21 (25.9%)	20 (23.8%)	21 (25.3%)	62 (25.0%)	15 (17.6%)
AE Related to Study Drug	7 (8.6%)	10 (11.9%)	14 (16.9%)	31 (12.5%)	8 (9.4%)
Grade \geq 3 AE Related to Study Drug	0	3 (3.6%)	0	3 (1.2%)	1 (1.2%)
SAE	24 (29.6%)	20 (23.8%)	20 (24.1%)	64 (25.8%)	16 (18.8%)
SAE Related to Study Drug	0	2 (2.4%)	0	2 (0.8%)	1 (1.2%)
AE Leading to Temporary Interruption of Study Drug	14 (17.3%)	8 (9.5%)	10 (12.0%)	32 (12.9%)	7 (8.2%)
AE Leading to Study Drug Discontinuation	7 (8.6%)	11 (13.1%)	12 (14.5%)	30 (12.1%)	8 (9.4%)
AE Leading to Death	0	1 (1.2%)	0	1 (0.4%)	0
All Deaths During Study	1 (1.2%)	1 (1.2%)	1 (1.2%)	3 (1.2%)	1 (1.2%)

Adverse events were mapped according to MedDRA Version 19
Treatment-emergent AEs are those started on or after first study dose date up to and including 30 days after permanent discontinuation, or led to premature study drug discontinuation
Toxicity grades (1=Mild, 2=Moderate, 3=Severe, 4=Life-Threatening, 5=Death) were from modified CTCAE Version 4.03

Table 1-4 presents a summary of AEs reported for \geq 5% of subjects in any treatment group by preferred term. The most common AEs in the pooled SEL group were upper respiratory tract infection, hypertension, hyperkalemia, diarrhea, constipation, and hypoglycemia, with no dose-dependent toxicity noted.

Table 1-4. GS US-223-1015: Adverse Events Occurring in \geq 5% of Subjects in Any Treatment Group by Preferred Term (Safety Analysis Set)

	SEL 2 mg (N = 81)	SEL 6 mg (N = 84)	SEL 18 mg (N = 83)	SEL Pooled (N = 248)	Placebo (N = 85)
Number (%) of Subjects Experiencing Any AE	64 (79.0%)	71 (84.5%)	63 (75.9%)	198 (79.8%)	71 (83.5%)
Upper respiratory tract infection	5 (6.2%)	5 (6.0%)	8 (9.6%)	18 (7.3%)	9 (10.6%)
Hypertension	9 (11.1%)	6 (7.1%)	3 (3.6%)	18 (7.3%)	6 (7.1%)
Hyperkalaemia	6 (7.4%)	4 (4.8%)	8 (9.6%)	18 (7.3%)	4 (4.7%)
Diarrhoea	8 (9.9%)	2 (2.4%)	7 (8.4%)	17 (6.9%)	4 (4.7%)
Anaemia	4 (4.9%)	6 (7.1%)	5 (6.0%)	15 (6.0%)	5 (5.9%)
Oedema peripheral	2 (2.5%)	5 (6.0%)	4 (4.8%)	11 (4.4%)	8 (9.4%)
Constipation	6 (7.4%)	7 (8.3%)	3 (3.6%)	16 (6.5%)	2 (2.4%)

	SEL 2 mg (N = 81)	SEL 6 mg (N = 84)	SEL 18 mg (N = 83)	SEL Pooled (N = 248)	Placebo (N = 85)
Nausea	8 (9.9%)	5 (6.0%)	1 (1.2%)	14 (5.6%)	4 (4.7%)
Acute kidney injury	3 (3.7%)	6 (7.1%)	6 (7.2%)	15 (6.0%)	2 (2.4%)
Back pain	3 (3.7%)	6 (7.1%)	6 (7.2%)	15 (6.0%)	2 (2.4%)
Hypoglycaemia	7 (8.6%)	5 (6.0%)	4 (4.8%)	16 (6.5%)	1 (1.2%)
Urinary tract infection	6 (7.4%)	1 (1.2%)	5 (6.0%)	12 (4.8%)	5 (5.9%)
Dyspnoea	1 (1.2%)	5 (6.0%)	6 (7.2%)	12 (4.8%)	3 (3.5%)
End stage kidney disease	2 (2.5%)	4 (4.8%)	3 (3.6%)	9 (3.6%)	6 (7.1%)
Chronic kidney disease	2 (2.5%)	5 (6.0%)	3 (3.6%)	10 (4.0%)	4 (4.7%)
Arthralgia	6 (7.4%)	1 (1.2%)	1 (1.2%)	8 (3.2%)	5 (5.9%)
Blood creatinine increased	6 (7.4%)	1 (1.2%)	3 (3.6%)	10 (4.0%)	2 (2.4%)
Cardiac failure congestive	3 (3.7%)	2 (2.4%)	5 (6.0%)	10 (4.0%)	2 (2.4%)
Cellulitis	1 (1.2%)	3 (3.6%)	6 (7.2%)	10 (4.0%)	1 (1.2%)
Dizziness	1 (1.2%)	1 (1.2%)	5 (6.0%)	7 (2.8%)	4 (4.7%)
Hyperglycaemia	6 (7.4%)	1 (1.2%)	3 (3.6%)	10 (4.0%)	1 (1.2%)
Metabolic acidosis	3 (3.7%)	1 (1.2%)	5 (6.0%)	9 (3.6%)	2 (2.4%)
Bronchitis	1 (1.2%)	1 (1.2%)	3 (3.6%)	5 (2.0%)	5 (5.9%)
Cough	3 (3.7%)	2 (2.4%)	5 (6.0%)	10 (4.0%)	0
Gout	3 (3.7%)	5 (6.0%)	0	8 (3.2%)	1 (1.2%)
Abdominal pain	0	5 (6.0%)	1 (1.2%)	6 (2.4%)	0

Adverse events were mapped according to MedDRA Version 19
Treatment-emergent AEs are those started on or after first study dose date up to and including 30 days after permanent discontinuation, or led to premature study drug discontinuation
Multiple AEs were counted once per subject for each PT. PTs are presented by descending order of the total frequency (all treatment groups combined)

Table 1-5 presents a summary of serious adverse events (SAEs) occurring in ≥ 2 subjects in any treatment group by preferred term. In the placebo group, 18.8% (16 subjects) experienced an SAE compared with 25.8% (64 subjects) in the pooled SEL group (29.6%, 23.8%, and 24.1% for SEL 2, 6, and 18 mg, respectively). The most common SAEs were acute kidney injury, congestive cardiac failure, pneumonia, chest pain, fluid overload, and hypertension, with no dose-dependent toxicity noted.

Table 1-5. GS-US-223-1015: Serious Adverse Events Occurring in ≥ 2 Subjects in Any Treatment Group by Preferred Term (Safety Analysis Set)

	SEL 2 mg (N = 81)	SEL 6 mg (N = 84)	SEL 18 mg (N = 83)	SEL Pooled (N = 248)	Placebo (N = 85)
Number (%) of Subjects Experiencing Any SAE	24 (29.6%)	20 (23.8%)	20 (24.1%)	64 (25.8%)	16 (18.8%)
Acute kidney injury	3 (3.7%)	3 (3.6%)	1 (1.2%)	7 (2.8%)	2 (2.4%)
Cardiac failure congestive	2 (2.5%)	1 (1.2%)	4 (4.8%)	7 (2.8%)	2 (2.4%)
Pneumonia	3 (3.7%)	2 (2.4%)	1 (1.2%)	6 (2.4%)	0
Chest pain	1 (1.2%)	2 (2.4%)	1 (1.2%)	4 (1.6%)	1 (1.2%)
Fluid overload	2 (2.5%)	1 (1.2%)	1 (1.2%)	4 (1.6%)	0
Hypertension	3 (3.7%)	0	1 (1.2%)	4 (1.6%)	0
Acute myocardial infarction	1 (1.2%)	2 (2.4%)	0	3 (1.2%)	0
Chronic obstructive pulmonary disease	3 (3.7%)	0	0	3 (1.2%)	0
Dyspnoea	0	2 (2.4%)	1 (1.2%)	3 (1.2%)	0
Bradycardia	2 (2.5%)	0	0	2 (0.8%)	1 (1.2%)
Cardiac failure acute	2 (2.5%)	0	0	2 (0.8%)	1 (1.2%)
Hypovolaemia	2 (2.5%)	0	0	2 (0.8%)	0
kidney failure	2 (2.5%)	0	0	2 (0.8%)	0
Cerebrovascular accident	0	0	0	0	2 (2.4%)

Adverse events were mapped according to MedDRA Version 19
Treatment-emergent AEs are those started on or after first study dose date up to and including 30 days after permanent discontinuation, or led to premature study drug discontinuation
Preferred terms are presented by descending order of the total frequency (all treatment groups combined)

Table 1-6 presents a summary of subjects with Grade 3 or 4 laboratory abnormalities. In the placebo group, 51.8% (44 subjects) experienced a Grade 3 or 4 laboratory abnormality compared with 51.2% (127 subjects) in the pooled SEL group (44.4%, 52.4%, and 56.6% for SEL 2, 6, and 18 mg respectively). The most common Grade 3 or 4 laboratory abnormalities were hyperglycemia and fasting hyperglycemia.

Table 1-6. GS-US-223-1015: Grade 3 or 4 Laboratory Abnormalities (Safety Analysis Set)

	SEL 2 mg (N = 81)	SEL 6 mg (N = 84)	SEL 18 mg (N = 83)	SEL Pooled (N = 248)	Placebo (N = 85)
Subjects with Post-baseline Value	81	84	83	248	85
Maximum Post-baseline Toxicity Grade					
Grade 3 or 4	36 (44.4%)	44 (52.4%)	47 (56.6%)	127 (51.2%)	44 (51.8%)
Grade 3	32 (39.5%)	39 (46.4%)	44 (53.0%)	115 (46.4%)	42 (49.4%)
Grade 4	4 (4.9%)	5 (6.0%)	3 (3.6%)	12 (4.8%)	2 (2.4%)

Toxicity grades (1=Mild, 2=Moderate, 3=Severe, 4=Life-Threatening, 5=Death) were from modified CTCAE Version 4.03
 For maximum post-baseline toxicity grade, the most severe graded abnormality from all tests was counted for each subject
 For each individual laboratory test, the most severe graded abnormality for that test was counted for a subject
 A treatment-emergent laboratory abnormality was defined as an increase of at least 1 toxicity grade from baseline at any time post-baseline up to and including the date of last study drug dose plus 30 days

1.2.3.2.5. Conclusion

This study did not meet the predefined efficacy endpoints, which did not account for the acute effects of SEL on eGFR. In post-hoc analyses, SEL demonstrated a dose-dependent reduction in decline of kidney function in subjects with advanced DKD. Differences in eGFR slope between Weeks 4 and 48 indicate that SEL may be efficacious in slowing the progression of DKD {Chertow 2019}.

Treatment with SEL was well tolerated and no dose-limiting toxicity was observed.

1.3. Rationale for This Study

Diabetes mellitus is the leading cause of CKD in the developed world, accounting for half of all incident cases of ESKD, the latter of which is associated with a 5-year survival of less than 40%. Approximately 13 million people in the United States (US) and European Union (EU) have concomitant CKD and T2DM. Approximately 10 million of these patients have CKD Stage 2-4 and the prevalence continues to increase in step with the increasing prevalence of T2DM and metabolic syndrome. Current standard of care (SOC) therapies for DKD (angiotensin converting enzyme inhibitors [ACEi] and angiotensin receptor blockers [ARB]) target glomerular hypertension and do not address the underlying pathological processes of chronic inflammation and oxidative stress that persist and drive disease progression through fibrosis. The continual decline in eGFR that occurs in many patients with DKD despite treatment with these approved therapies highlights the large unmet medical need.

Selonsertib is a potent and selective once daily, orally administered inhibitor of ASK1 that has the potential to improve pathological sequelae in the kidney leading to GFR decline. SEL is expected to delay the time to development of serious adverse clinical outcomes such as kidney transplantation, dialysis, and death in patients with DKD. SEL has demonstrated clinical activity and a favorable safety and tolerability profile in a Phase 2 study in subjects with Stage 3 and 4 DKD.

In the Phase 2 study in subjects with Stage 3 and 4 DKD, subjects receiving SEL 18 mg had a larger acute decrease in eGFR (approximately 10% of the baseline value at Week 4) than the other SEL dose groups or placebo group, which may be due, in part, to greater inhibition of the kidney transporters involved in the secretion of creatinine by SEL at this higher dose (Studies GS-US-223-0102 and GS-US-223-3973). In a Phase 1b study in subjects with CKD with a eGFR between 20 to < 60 mL/min/1.73 m² (GS-US-223-0110), acute reversible decreases for both eGFR and mGFR were observed with SEL 18 mg, indicating a potential secondary mechanism involved in the acute decrease observed in eGFR upon initiation of SEL.

Due to this acute (potentially artefactual) effect observed in prior studies, this Phase 2b study has incorporated a Run-in design to account for the acute eGFR effect in order to better characterize the chronic (long-term) effect of SEL on eGFR. To maintain the integrity of the study, other than eGFR values < 15 mL/min/1.73 m², eGFR results collected at Visits A, B, C, and Visit 1 will not be released to subjects, investigators or sponsor before study unblinding. All eGFR values starting at week four will be released to subjects, investigators and the sponsor for safety monitoring and treatment decisions.

1.4. Rationale for Dose Selection of Selonsertib

A SEL dosing regimen of 18 mg once daily was selected for evaluation in this Phase 2b DKD study based on results from the dose-ranging Phase 2 studies in subjects with DKD, NASH, and PAH and an examination of pharmacokinetic/pharmacodynamic (PK/PD) relationships between SEL exposure and response.

[figure not shown]
Across the clinical development program, SEL administered for up to 48 weeks has been well tolerated with no clear exposure relationship for the incidence or severity of adverse events or laboratory abnormalities. Collectively, the efficacy, safety, and PK/PD data support evaluation of a single dose of SEL 18 mg in the proposed Phase 2b study in subjects with DKD.

Dose selection for SEL in the Phase 2bDKD study was based on results from the dose-ranging Phase 2 study in subjects with DKD indicating near maximal inhibition of p38 phosphorylation in blood cells, and near maximal slowing of the chronic rate of eGFR decline between week 4 and 48 of treatment. In addition, the percent change from baseline in phosphorylation of ASK-1 was measured in whole blood lysates with a sandwich immunoassay using anti-phospho-ASK-1 antibody to capture phospho-ASK-1 (p-ASK-1) and anti-ASK-1 antibody for detection. This was determined at Week 12 with all remaining samples from study GS-US-223-1015 (N = 126: 35, 28, 33, 30 from the placebo, 2 mg, 6 mg, and 18 mg daily SEL treatment arms, respectively) and provides additional data supporting the 18 mg dose of SEL. As the p-ASK-1 analysis was conducted on a subset of samples from the dataset previously presented in the IB, PK/PD analyses for both % phospho-p38 (p-p38) and p-ASK-1 have been reconstructed in this subset for a direct comparison to the observed p-ASK-1 results (Figure 1-4).

Across the range of SEL doses evaluated, a consistently greater degree of inhibition of the more proximal measure of ASK-1 engagement, %p-ASK-1, is observed compared to %p-p38 (Figure 1-4). Pharmacokinetic/pharmacodynamic model fits for %p-ASK-1 and %p-p38 in this analysis set indicate the maximum predicted inhibition of ASK-1 and p-38 phosphorylation to be

89.6% and 75.8%, respectively, with SEL exposure resulting in half-maximal inhibition of 185 hr*ng/mL and 1520 hr*ng/mL, respectively. These analyses of ASK-1 engagement support dose selection of 18 mg SEL which provides near maximal effect and any further increased dose of SEL is not expected to provide meaningfully greater PD response, or increased efficacy.

Figure 1-4. PK/PD Relationships for SEL Exposure (AUC_{tau}) and %p-p38 or %p-ASK-1 (Study GS-US-223-1015)

Similar to p38 phosphorylation, in the Phase 2 DKD study, a dose- and exposure (AUC_{tau})-dependent response relationship was observed for the rate of eGFR decline (slope) from Week 4 to 48. The mean eGFR slope in the 18 mg group was -1.27 mL/min/1.73 m²/year, significantly smaller than the placebo group slope (-4.97 mL/min/1.73 m²/year), and residing on the flat portion of the dose- and exposure-response curves. Additionally, the relationship between p-p38 inhibition and chronic eGFR slope by dose group showed a trend in improved efficacy with increasing dose of SEL with minimal overlap between SEL 18 mg and placebo.

In the Phase 2 DKD study, there was a small difference in change in eGFR between the 6 mg and 18 mg doses of SEL that trended in favor of the 18 mg dose at 48 weeks but was not statistically significant. This improvement with the 18 mg dose in slowing the rate of eGFR decline may be clinically significant over longer periods of time. For example, for patients starting with an eGFR of 30 mL/min/1.73 m², this difference between doses would increase time to kidney failure from approximately 4 years with SEL 6 mg to approximately 6 years with SEL 18 mg. In the context of such large therapeutic differences and a disease course that spans many years, SEL 18 mg is the optimal dose for the long-term prevention of kidney failure among patients with moderate to advanced DKD.

Across the clinical development program, SEL administered for up to 48 weeks has been well tolerated with no clear exposure relationship for the incidence or severity of adverse events or laboratory abnormalities. Collectively, the efficacy, safety, and PK/PD data support evaluation of SEL 18 mg in this Phase 2b study in subjects with DKD.

1.5. Rationale for Placebo Use

All subjects, including those randomized to the placebo arm, will continue to receive standard of care therapy (e.g., ACEi, ARB, etc.) as part of their treatment for T2DM and moderate to advanced DKD. Thus, the use of placebo will not interfere with their current treatment plan.

1.6. Risk/Benefit Assessment for the Study

Chronic kidney diseases, including DKD, are serious diseases that have broad and negative public health, social, and economic impacts. New agents that prevent long-term decreases in kidney function are needed to improve the efficacy, safety, and tolerability of treatments for these diseases.

This study will provide additional information regarding the safety and efficacy of SEL in patients with T2DM and moderate to severe DKD. Transient increases in serum creatinine have been observed in a dose-dependent manner with SEL and are consistent with the inhibitory effect of SEL on transporters involved in tubular creatinine secretion (MATE1 and MATE2K, $IC_{50} = 2.4 \mu\text{M}$ and $0.94 \mu\text{M}$). The potential benefits of SEL for the treatment of DKD were shown in the Phase 2 study GS-US-223-1015. SEL appeared to be safe and well-tolerated without significant dose-related toxicity and demonstrated a clinically meaningful reduction in decline of kidney function among subjects with advanced DKD. Differences in eGFR slope between SEL and placebo from 4 to 48 weeks demonstrate that SEL is expected to slow the progression of DKD. These data support further evaluation of the 18 mg dose in a Phase 2b study. No events considered to be adverse drug reactions (ADRs) to SEL have been identified in the clinical studies conducted to date. Thus, at this time, no significant clinical risks are expected with administration of SEL.

Potential risks of this study include those related to the fact that SEL is a new chemical entity. Although a long term safety profile has yet to be established, SEL, administered at doses up to 100-mg in Phase 1 studies and up to 18 mg in Phase 2 studies in subjects with NASH, AH, DKD, or PAH, appears to be well tolerated.

A concentration QT analysis demonstrated that SEL at doses up to 100-mg did not cause clinically relevant prolongation of the QTc interval. To mitigate the potential risk of liver injury, subjects are monitored closely; defined rules for close observation and drug cessation due to elevated liver tests are specified in the protocols. In addition, embryofetal toxicity was observed in nonclinical studies; therefore to prevent potential fetal exposure, adherence to highly effective methods of contraception will be required.

Additional risks to study subjects include those attributable to study participation in general, including risks associated with frequent clinic visits and laboratory blood draws, and the associated pain and discomfort of phlebotomy. Strategies to mitigate these risks include close monitoring of lab values as well as AEs. Parameters for discontinuation of the study drugs due to AEs and non-kidney laboratory abnormalities are also defined and will be closely followed.

For this study, frequent assessments of kidney function will be performed from the collection of both blood and urine samples. Parameters for discontinuation of the study drugs due to adverse events are defined in this study protocol and will be closely followed.

While the potential benefits and risks described above must be confirmed, available data in DKD subjects treated for 48 weeks, as well as the favorable safety profile seen across the Phase 2 studies in NASH, DKD, and PAH, provide strong rationale for a favorable benefit/risk ratio in support of the study in subjects with DKD.

1.7. Compliance

This study will be conducted in compliance with this protocol, Good Clinical Practice (GCP), and all applicable regulatory requirements.

2. OBJECTIVES

The primary objective of this study is:

- To evaluate whether SEL can slow the decline in kidney function

The secondary objectives of this study are:

- To evaluate whether SEL can reduce the risk of kidney failure, or reduce the risk of death due to kidney disease in subjects with diabetic kidney disease (DKD)
- To assess the safety and tolerability of SEL in subjects with DKD

CCI [REDACTED]

[REDACTED]

[REDACTED]

[REDACTED]

[REDACTED]

[REDACTED]

3. STUDY DESIGN

3.1. Endpoints

Primary efficacy endpoint:

eGFR_{cr} slope from treatment-specific baselines

The secondary endpoints of this study are:

- Proportion of Kidney Clinical Events at Week 48 defined as any of the following events:

Confirmed $\geq 40\%$ decline in eGFR_{cr} from pre-run-in baseline, or

Kidney failure (dialysis performed for at least 4 weeks, kidney transplantation, or confirmed decrease in eGFR_{cr} to < 15 mL/min/1.73 m² for subjects without dialysis or kidney transplantation), or

Death due to kidney disease

- Time from randomization to first occurrence of a Kidney Clinical Event
- eGFR_{cys} slope from pre-run-in baseline

CCI [REDACTED]

- [REDACTED]
- [REDACTED]
- [REDACTED]
- [REDACTED]
- [REDACTED]
- [REDACTED]
- [REDACTED]
- [REDACTED]
- [REDACTED]
- [REDACTED]

[figure not shown]

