3.2. Study Design

This is a Phase 2b, randomized, double-blind, placebo-controlled, parallel group, multicenter study evaluating the efficacy and safety of SEL in subjects with T2DM and moderate to advanced DKD.

Subjects meeting the study’s entry criteria after signing the informed consent will enroll into a Run-in period of at least 5 weeks and receive at least one week of placebo to match (PTM) and then SEL (18 mg) for at least 4 weeks. After completing the Run-in period, subjects meeting eligibility will be randomized in a 1:1 ratio to receive SEL (18 mg) or PTM orally once daily. Subjects must be on SEL for at least 7 consecutive doses prior to Visit C and Visit 1 in order to randomize.

The overall study design is presented graphically in [Figure 3-1](#).

Figure 3-1. Study Design Schema

- Abbreviations: EOS = End of Study, EOT = End of Treatment, PTM = placebo-to-match to match, SEL= Selonsertib
- Prior to randomization, subjects must have at least 7 consecutive daily doses of study drug immediately prior to Visit C and Randomization (Visit 1)
 - Post-run-in baseline eGFR is defined as the average of Visit C and Visit 1 eGFR values. Pre-run-in baseline is defined as the average of Visit A and Visit B eGFR values.
 - If kidney failure is reached, subjects should discontinue study drug and remain on study.
 - If a subject permanently discontinues study drug, there will be a 30 Day EOT Follow-up visit. Subjects who permanently discontinue study drug prior to the global study end date will have an EOT visit and a 30 Day (± 7 days) EOT Follow-up visit. Subjects are encouraged to complete all remaining study visits until the global study end date.
 - The global study end date will occur when the last randomized subject reaches 48 weeks and/or all subjects on study have completed end of study assessments and the 30 Day EOS Safety Follow-up visit.

Randomization will be stratified by average eGFR values from Visit A and Visit B, average urine albumin to creatinine ratio (UACR) values from Visit A and B, and concomitant use of sodium-glucose co-transporter-2 (SGLT-2) inhibitors at Visit 1.

Subjects will continue to receive SEL or PTM in a double-blind fashion until death, study drug discontinuation, kidney failure (dialysis performed for at least 4 weeks, kidney transplantation, or confirmed decrease in eGFR to $< 15 \text{ mL/min/1.73 m}^2$ for subjects without dialysis or kidney transplantation), or the global study end date.

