8.5.2. Secondary Analyses

The Secondary Analysis Set for efficacy analyses is the ITT Analysis Set.

8.5.2.1. Analysis of proportion of Kidney Clinical Events at Week 48

Kidney Clinical Event is defined as any of the following events:

- Confirmed ≥ 40% decline in eGFR_{cr} from baseline, or
- Kidney failure (dialysis performed for at least 4 weeks, kidney transplantation, or confirmed decrease in eGFR_{cr} to < 15 mL/min/1.73 m² for subjects without dialysis or kidney transplantation), or
- Death due to kidney disease

The ≥ 40% decline in eGFR_{cr} from baseline and sustained decrease in eGFR_{cr} to < 15 mL/min/1.73 m² components need to be confirmed at the next scheduled visit but at least 4 weeks after the index measurement. Events of eGFR_{cr} < 15 mL/min/1.73 m² or eGFR_{cr} decline ≥ 40% from baseline without confirmation due to study discontinuation (e.g., death or lost to follow-up) will be included in the analysis.

The analysis of proportion of Kidney Clinical Events will be conducted when all subjects in the ITT Analysis Set reach Week 48 Visit or discontinue from the study. Number and proportion of subjects who experience a Kidney Clinical Event will be summarized. The Cochran-Mantel-Haenszel (CMH) approach adjusting for stratification factors will be used for hypothesis testing of Kidney Clinical Events.

Number and proportion of subjects who experienced each component of the Kidney Clinical Events will also be summarized.

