6.2. Secondary Endpoints

6.2.1. Definition of Secondary Endpoints

Secondary endpoints for this study are:

- Proportion of Kidney Clinical Events defined as any of the following events:
 - Confirmed $\geq 40\%$ decline in eGFR_{cr} from pre-run-in Baseline, or
 - Kidney failure (dialysis performed for at least 4 weeks, kidney transplantation, or confirmed decrease in eGFR_{cr} to < 15 mL/min/1.73 m² for subjects without dialysis or kidney transplantation), or
 - Death due to kidney disease

The $\geq 40\%$ decline in $eGFR_{cr}$ from Baseline and sustained decrease in $eGFR_{cr}$ to <15 mL/min/1.73 m² components need to be confirmed at the next scheduled visit but at least 4 weeks after the index measurement (i.e., the first measurement of $\geq 40\%$ decline in $eGFR_{cr}$ from Baseline or $eGFR_{cr} < 15$ mL/min/1.73 m²). Events of $eGFR_{cr}$ decline $\geq 40\%$ from Baseline or $eGFR_{cr} < 15$ mL/min/1.73 m² without confirmation due to study discontinuation (e.g., death or lost to follow-up) will be included in the analysis and counted as events. Date of the index measurement will be used as the date of event in the analysis.

- Time from randomization to first occurrence of a Kidney Clinical Event

If a subject has not experienced any Kidney Clinical Events at the time of global study end date/early discontinuation of the study, this subject will be censored at the time of the last assessment of kidney function.

- $eGFR_{cys}$ slope from pre-run-in Baseline through Week 84

The values for $eGFR_{cys}$ will be calculated using the CKD-EPI Cystatin C Equation (2012):

$$eGFR = 133 \times \min\left(\frac{S_{cys}}{0.8}, 1\right)^{-0.499} \times \max\left(\frac{S_{cys}}{0.8}, 1\right)^{-1.328} \times 0.996^{Age} \times 0.932[if\ female]$$

S_{cys} = standardized serum cystatin C (mg/L)

min indicates the minimum of $S_{cys}/0.8$ or 1

max indicates the maximum of $S_{cys}/0.8$ or 1

age in years

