6.2.2.1. Analysis of proportion of Kidney Clinical Events

Number and proportion of subjects who experience a Kidney Clinical Event will be summarized by treatment group. Number and proportion of subjects who experienced each component of the Kidney Clinical Events will also be summarized by treatment group. 95% exact CI based on the Santner-Snell method (Santner and Snell, 1980) will be presented for the difference in proportions between SEL and placebo arms for the Kidney Clinical Events endpoint, as well as each component of the Kidney Clinical Events.

P-value based on the Cochran-Mantel-Haenszel (CMH) approach adjusting for randomization stratification factors will be reported for the comparison of proportion of Kidney Clinical Events between treatment arms. In addition, p-value based on Fisher's exact test without adjusting for randomization stratification factors will also be reported. P-values will not be reported for the comparison of each component of the Kidney Clinical Events endpoint between treatment arms.

Subjects who do not have sufficient measurements to determine whether or not they had a Kidney Clinical Event will be considered not having a Kidney Clinical Event.

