- Sensitivity analysis to evaluate the impact of attenuation of the acute effect. For subjects in the SEL group, the on-treatment $eGFR_{cr}$ values will be adjusted using a regression model as described in [Appendix 2](#), which takes into account attenuation of the acute treatment effect that may be due to the theoretical concern for loss of kidney function over time. This adjusted on-treatment $eGFR_{cr}$ value will be compared with the pre-run-in Baseline $eGFR_{cr}$ to calculate an adjusted percent $eGFR_{cr}$ reduction. For subjects in the placebo group, percent $eGFR_{cr}$ reduction will be calculated by comparing observed $eGFR_{cr}$ values with the pre-run-in Baseline $eGFR_{cr}$.
- Sensitivity analysis in subjects who completed study treatment.
- Sensitivity analysis excluding subjects with randomization stratification mismatch between IXRS and Clinical Database.
- Sensitivity analysis excluding subjects who took prohibited medications that may affect SEL efficacy or decrease SEL drug level in the prohibited period as detailed in [Appendix 3](#).

- Sensitivity analysis where a 57% reduction in $eGFR_{cr}$ from pre-run-in Baseline will be used for the $eGFR_{cr}$ reduction component of the Kidney Clinical Events instead of 40% reduction.
- Sensitivity analysis for the Kidney Clinical Events based on $eGFR_{cys}$. The Kidney Clinical Events endpoint will have the same definition as in Section 6.2.1, except that the $eGFR$ reduction and $eGFR < 15$ components will be based on $eGFR_{cys}$ instead of $eGFR_{cr}$.

The same approaches as described in Sections 6.2.2.1 only will be used for hypothesis testing for Kidney Clinical Events for the following:

- The proportion of Kidney Clinical Events by Week 48 will be compared between SEL and placebo treatment arms. Subjects who do not have sufficient measurements to determine whether or not they had a Kidney Clinical Event by Week 48 will be considered not having a Kidney Clinical Event by Week 48.

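### The protocol fixes the Kidney Clinical Event proportion at Week 48; the SAP drops the time point and tests a crude proportion over follow-up that differs between subjects

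*Protocol*

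**What the plan says.** **Protocol.** Section 3.1 defines the first secondary endpoint as "Proportion of Kidney Clinical Events at Week 48 defined as any of the following events". The heading of 8.5.2.1 repeats the horizon: "Analysis of proportion of Kidney Clinical Events at Week 48". On timing, "The analysis of proportion of Kidney Clinical Events will be conducted when all subjects in the ITT Analysis Set reach Week 48 Visit" or have discontinued.

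**SAP.** Section 6.2.1 gives the endpoint as "Proportion of Kidney Clinical Events defined as any of the following events", with the same three components and no horizon. Section 6.2.2.1 sets the test: "P-value based on the Cochran-Mantel-Haenszel (CMH) approach adjusting for randomization stratification factors will be reported for the comparison of proportion of Kidney Clinical Events". It adds Fisher's exact test and an exact 95% CI for the difference. None of these has a cut-off or an allowance for time at risk. On missing information: "Subjects who do not have sufficient measurements to determine whether or not they had a Kidney Clinical Event will be considered not having" one.

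The Week 48 version is still planned. At the end of 6.2.2.2, after the list introduced as sensitivity analyses, the SAP states: "The proportion of Kidney Clinical Events by Week 48 will be compared between SEL and placebo treatment arms". It uses the 6.2.2.1 methods and the same rule for undetermined subjects.

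**Follow-up.** Protocol 3.2: "The global study end date will occur when the last randomized subject reaches 48 weeks". Earlier subjects are therefore followed for longer. SAP 2.2 runs the final analysis after all subjects have completed the study. SAP 6.1 sets the primary slope at Week 84 with a sensitivity analysis to Week 96, and Table 3-2 has visit windows up to Week 168.

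**Error rate.** SAP 3.5 tests every secondary and other efficacy endpoint at one-sided 0.15 without multiplicity adjustment.

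**The concern.** The two documents define different quantities under one endpoint name. A proportion by Week 48 is a risk over a stated period. A proportion over whatever follow-up each subject had is an average of risks over different periods, weighted by how quickly subjects were enrolled. The same drug in the same disease would give another value under another accrual pattern.

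Two things are at stake. First, the secondary result and its confidence interval could not be read as a risk at any time, or compared with another trial. Second, a longer and variable observation period gives dropout more time to act, and subjects who cannot be classified are scored as event-free. If one arm loses more subjects, its event proportion falls for that reason alone.

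**Working it through.** **Figures in the plan.** The documents give no event rate, event count, power or accrual pattern for this endpoint. The only stated power (99%, or 97% after dropout) concerns the creatinine-based eGFR slope. It reproduces as 98.5% and 97.2%, and it does not bear on this point. Every rate below is an assumption.

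**1. What the crude proportion estimates.** Assume risk r by Week 48, constant hazard λ = −ln(1 − r)/48 per week, and follow-up uniform from 48 to F weeks. A subject followed for t weeks has risk 1 − exp(−λt). The pooled proportion is

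1 − [exp(−48λ) − exp(−Fλ)] / [λ(F − 48)].

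With r = 20%, 48λ = 0.2231:

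- Fixed at Week 48: 20%.
- F = 96: 1 − (0.800 − 0.640)/0.2231 = 28%.
- F = 168: 1 − (0.800 − 0.458)/0.5579 = 39%.

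Individual risk would be 32% at Week 84 (1 − 0.8^(84/48)) and 54% at Week 168 (1 − 0.8^(168/48)). The pooled figure lies below the individual risk at the longest follow-up, because it averages over subjects with less.

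**2. The between-arm difference.** With an assumed 10% placebo risk by Week 48, hazard ratio 0.7, 150 per arm and one-sided 0.15:

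| Quantity | Placebo | SEL | Difference (points) | Power |
|---|---|---|---|---|
| By Week 48 | 10.0% | 7.1% | 2.9 | 44% |
| Crude, 48–96 weeks | 14.6% | 10.5% | 4.1 | 52% |
| Crude, 48–168 weeks | 20.9% | 15.2% | 5.7 | 60% |

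One drug effect gives three differences, set by the length of follow-up. For placebo risks of 6% to 15%, the Week 48 difference is 1.8 to 4.2 points; the crude difference is 2.6 to 7.8 points across the two follow-up ranges.

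**3. Error rate of the test with no drug effect.** This used 5,000 simulated trials per setting, 10% risk by Week 48, an unstratified pooled z test, and subjects who drop out before an event counted as event-free. The nominal rate is 0.15 and the simulation standard error is about 0.005.

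| Dropout per 48 weeks (placebo, SEL) | Crude, 48–96 | Crude, 48–168 | By Week 48 |
|---|---|---|---|
| None | 0.149 | 0.150 | 0.151–0.162 |
| 15%, 15% | 0.149 | 0.155 | 0.154–0.161 |
| 22.4%, 28.9% | 0.207 | 0.236 | 0.174–0.175 |

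The Week 48 column shows the range over two separate runs. The unequal rates are the study-drug discontinuation rates for placebo and SEL 18 mg in the earlier Phase 2 study (Protocol 1.2.3.2.2), borrowed here as study dropout. In that setting the mean observed proportions, placebo against SEL, were 12.1% against 11.4% (crude, to 96 weeks), 15.8% against 14.5% (crude, to 168 weeks) and 8.8% against 8.5% (Week 48). The spurious gaps are 0.7, 1.3 and 0.3 points.

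**The case against.** Much of the case on the other side stands.

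- **The Week 48 comparison is not lost.** SAP 6.2.2.2 prespecifies it with the same methods. With no hierarchy and one-sided 0.15 throughout, its position has little inferential effect. A reader might infer that the protocol's endpoint was deleted; the SAP does not support that. What changes is which version carries the secondary label.
- **Accrual does not bias the test.** A reader might infer that unequal follow-up invalidates the comparison. Under 1:1 randomization administrative follow-up is balanced, and the crude test held its nominal rate with no dropout or equal dropout.
- **The dropout figures show direction only.** Stopping drug is not leaving the study. Protocol 3.4 and 6.7 keep such subjects on study, and remote contact still captures death, dialysis and transplant. SAP 6.2.1 also counts threshold crossings left unconfirmed because of study discontinuation. However, the remote list in 6.7.3 includes no eGFR, so the eGFR-based components can still go unobserved. The Week 48 version shares the event-free rule, so restoring it lessens this exposure without removing it.
- **Something is gained by using all follow-up.** More events gave 52% to 60% power against 44% in the example. A reader might infer that the change has no benefit; that would be wrong.
- **Week 168 is the last row of a window table.** It does not show that any subject is followed that long.
- **Redaction.** SAP text after 6.2.2.3 is blacked out and may explain the change.

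None of this gives the proportion in SAP 6.2.1 a time point.

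**Conclusion.** The point holds for the definition and interpretation of the secondary endpoint. The protocol specifies a Week 48 risk; the SAP puts in its place a proportion over unequal follow-up and leaves the Week 48 comparison with the sensitivity analyses. The resulting estimate, difference and interval describe no defined period, and they are more sensitive to unequal dropout.

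The size can only be illustrated: about 28% or 39% pooled against 20% at Week 48, given the assumed risk, constant hazard and uniform follow-up. A reader might take 54%, the individual risk at Week 168, as a possible reported value. It is not one: the study ends when the last randomized subject reaches 48 weeks, so subjects with less follow-up pull the pooled figure down.

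The documents do not support a claim that the between-arm test is biased by accrual, or that the change is undocumented. The mismatch should be corrected, and settled before unblinding because each secondary endpoint is tested at an unadjusted one-sided 0.15.

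**What to change.** In SAP 6.2.1 and 6.2.2.1, state the secondary endpoint as the proportion with a Kidney Clinical Event by Week 48, and make its CMH comparison the secondary test. Move the all-follow-up proportion to the sensitivity list in 6.2.2.2. Leave events after Week 48 to the stratified log-rank and Cox analysis, which already uses all follow-up with censoring.

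If the sponsor prefers the all-follow-up version, the minimum is to state the departure from the protocol with its reason and to label that proportion as supportive.

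The cost is SAP wording, since both analyses are already planned. The downside is fewer events and somewhat lower power in this one test (44% against 52% to 60% under the assumptions above), offset by the time-to-first-event endpoint.
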